Hispanic cancer patients in the U.S. also report significantly worse cancer-related symptom burden and health-related quality of life (HRQOL) than NHWs, even after adjusting for socioeconomic factors.^{3,4} Despite this, very few randomized, intervention studies have specifically targeted cancer-related symptom burden and HRQOL outcomes among Hispanic women, especially during the period at the end of active treatment which is a critical period to intervene to provide skills and tools to assist with the transition to survivorship⁵. The few, existing studies were too small and underpowered to detect differences or yielded null findings^{6,7}. One study did report a positive effect, however which components or combination components of psychosocial interventions that may reduce symptom burden and improve HRQOL in Hispanic breast cancer survivors (BCS) remains unknown, thus creating a critical gap in the literature⁸. Hispanic women diagnosed with cancer may have difficulty gaining access to supportive and psychosocial services that can assist with symptom burden and HRQOL and face obstacles such as cost, lack of insurance coverage, time constraints to name a few^{1,11}. Therefore innovative approaches to providing interventions such as Smartphone technology are especially important for this patient population. Ubiquitous Smartphone use among ethnic minorities in the US provide a unique opportunity to implement a pragmatic technology- and evidence-based psychosocial intervention that overcomes some access to care barriers as well as time and logistical constraints¹². Given that Hispanics own Smartphones and seek health information online from a mobile device at similar or higher rates than other groups in the U.S., Smartphone interventions offer an opportunity to overcome obstacles to accessing resources and services that can be culturally informed and provide skills to improve symptom burden and HRQOL¹². We have previously shown that cancer-related knowledge, stress management, coping skills, and communication can negatively affect the post-treatment survivorship phase, underscoring the importance addressing these components in a psychosocial intervention^{3,13,14}.

3.0 Inclusion and exclusion criteria:

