Aim 2 (Phase 2): Optimize components for Mi Guia through a 6-week randomized trial to evaluate the efficacy of Mi Guia relative to a smartphone application on health education (My Health), our control condition. Participants will complete the same procedures regardless of randomization assignment to help minimize potential confounding factors during the intervention or control delivery. Participants will be early-stage women completing active treatment (n= 90), see eligibility criteria above. A

minimum of 25 participants will meet the compromised cancer-related symptom burden and HRQOL. We hypothesize that Hispanic BCS will find the smartphone application, My Guide, an acceptable and feasible way of accessing post-treatment relevant information. Furthermore, we expect that, in comparison to the control condition, My Guide will have a measurable, positive impact on this population's HRQOL and cancer-specific distress.

Participants will be individually randomized, 1:1, to the health promotion application (control condition) or to the My Guide application (intervention condition). A longitudinal mixed effects linear model will be fit with the outcome (the Functional Assessment of Cancer Therapy-Breast; FACT-B) score as the dependent variable. Type of treatment (e.g., surgery type, hormonal therapy), time since completion of active treatment, stage of diagnosis, education, marital status, language, comorbidities and age at diagnosis will be examined for their associations with study outcomes for potential entry as covariates in the statistical model. Effect sizes will be calculated by dividing by the baseline standard deviation. The potential moderating effect will be examined by entering interaction terms into the model. Similar models will be fit to examine the subscales of the FACT-B. A total of 90 participants will be randomly assigned to one of 2 conditions (control or intervention), resulting in 45 participants per condition. The main effect of each intervention component will be evaluated by comparing the outcomes for participants who receive the intervention (n= 45) to those who did not receive the intervention (control; n=45), allowing a comparison of main effects. Participants will be compensated \$100 and reimbursed up to \$22 for travel and data usage.

Technology.

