After six weeks of active application use and telecoaching in the intervention or control conditions, participants will complete two follow-up appointments. At the end of week six, they will complete their first follow-up meeting, they will complete an assessment consisting of the same questions from the baseline questionnaire, as well as an exit interview (the baseline questionnaire, and exit interviews were previously used in Aim 1c of this study). The duration of the meeting is estimated to be under one hour. This meeting can be completed over the phone, or in person at Northwestern depending on the participant's request.

Two weeks later, we will contact participants for a final 30-minute long assessment consisting of the same questions from the baseline which measure our primary outcomes and intervention targets. Participants will **not** be expected to use the phone application, and will not receive telecoaching calls during the 1st follow-up and the 2nd follow-up period.

Participants also have the option of coming to our office at Northwestern for our last meeting. If they choose to come to Northwestern for the final meeting, they can have their compensation in cash rather than receiving the amount in a gift card via mail.

We will first submit all English versions of our Aim 2 documents and application content to the IRB. Once the English versions of the documents are approved, we will submit final clean versions of the Spanish documents. This will help minimize back-and-forward resubmission of documents due to any changes requested prior to final approval.

After the 8 weeks, participants will have the opportunity to receive the application they did not have

access to during the trial. We would like to make sure that even participants that were not assigned the intervention application (My Guide) have the opportunity to learn from it if they want to. Similarly, it is possible that the My Health application will be useful for My Guide participants. Participants will be promised access to the other application for 8 weeks.

We cannot promise indefinite access to either of the study applications since we are not sure of the cost to host the applications long-term. However, if a participant wants to continue to use either application, we will allow them to keep it, but we will inform them that they could lose access to the application at any time after the initial 8 weeks.

Cultural Awareness.

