Upon meeting study eligibility, participants will be scheduled for an in-person visit at our laboratory space in the Department of Medical Social Sciences, or at a location of their choice if travel to the university is not feasible, where they will be provided additional information on the study (e.g., risks, benefits, procedures). We will assure that participants have a full understanding of the written informed consent by asking them several questions to ascertain comprehension (e.g., what is your understanding of the purpose of the study? Can you briefly explain to us what is expected of you? Can you please tell us what are the risks involved? The benefits involved?). We have used this approach in the past and it has helped us ascertain that our participants fully understand all procedures, and

provides us with an opportunity to clarify or answer any questions. In order to minimize the possibility of coercion or undue influence, all study staff who are involved in the consent process will repeatedly remind potential participants that their participation is voluntary and that participation or lack of participation in the study is not related to the receipt of their medical care.

Written consent will be obtained for each aim of the study. Women participating in the longitudinal aspects of the study (i.e., Aims 1c and 2) will only be asked to complete consent one time. Only the PI, CO-Is, and trained members of the study staff will be able to consent participants. We anticipate that the consent process will take between 15-20 minutes for Aims 1a and 1b and 20-25 minutes for Aims 1c and 2 as these aims will require additional explanation regarding the longitudinal intervention.

All participants will have the choice to complete the consent form in English or Spanish. Participants who request to complete the consent in Spanish will be consented by a fully bilingual members of the research team. Consent will be translated into Spanish by [name]. [name] is a native Spanish speaker and is IRB-certified to translate documented from English into Spanish.

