There is a slight risk of loss of confidentiality. While any information transmitted through the application is protected (see data security section), there is some possibility that others may see participants open the application on the smartphones. We have included language in the consent reminding participants of this potential risk. Although the application does not collect any identifiable information except for the email address during login, if they have privacy concerns, they are instructed to use the application in private.

One final foreseen risk is that patients occasionally try to access the smartphone or participate in assessments while walking or driving. Risks associated with cell phone use and walking or driving will be managed by informing the participants that they are not permitted to use the phones while driving or walking.

We do not anticipate the need to withdraw participants from any of the study aims without their consent. All study data that is already collected, including screening data, will be considered usable data in the event that a participants voluntarily withdraws from the study.

There are no risks associated with participation in Aim 1d for community stakeholder participants.

10.0 Potential Benefits to Participants:

Participants in Aims 1a and 1b will not receive any direct benefit from study participation. However, we have found in our previous work that participants have often expressed gratitude for the opportunity to share their cancer-related experiences and to have the opportunity to contribute to research that may benefit other patients with cancer.

Participants in Aim 1c and Aim 2 will most likely benefit from the intervention content that is designed to improve health-related quality of life and reduced symptom burden. The magnitude of this potential benefit is expected to be moderate to high with a potential duration of several years.

Participants randomized to health control in Aim 2 will benefit from learning more about breast cancer and healthy living (e.g., diet, exercise, nutrition). In our previous research, we have found that former cancer patients have reported medium to high satisfaction with learning about healthy living and have reported that they have been able to incorporate the information on healthy living into their everyday routines.

There are no benefits associated with participation in Aim 1d for community stakeholder participants.

11.0 Financial Compensation:

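### Section 10.0 presents as likely, sizeable and long-lasting the benefit that Aim 2 is meant to test; if women hear this, expectancy could favour My Guide on unblinded self-reported outcomes

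*Combined protocol and SAP*

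**What the plan says.** Section 10.0 (Potential Benefits to Participants) opens its account of the trial phases with "Participants in Aim 1c and Aim 2 will most likely benefit from the intervention content", and describes that content as aimed at quality of life and symptom burden. It continues: "The magnitude of this potential benefit is expected to be moderate to high with a potential duration of several years". A separate paragraph covers controls: "Participants randomized to health control in Aim 2 will benefit from learning more about breast cancer and healthy living". It adds that former patients have been satisfied with healthy-living material, but names no gain in quality of life and no size or duration.

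Section 1.0 lists symptom burden and quality of life as the primary outcomes. The Aim 2 text in Section 4.0 gives the hypothesis that, compared with control, "My Guide will have a measurable, positive impact on this population's HRQOL and cancer-specific distress". On the prior evidence, Section 2.0 says that the few existing studies "were too small and underpowered to detect differences or yielded null findings", and then mentions one positive study.

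Section 7.0 (Consent Process) has staff give information that includes benefits and confirm understanding "by asking them several questions to ascertain comprehension". One example reads "Can you please tell us what are the risks involved? The benefits involved".

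**The concern.** The protocol describes as probable the effect that the trial exists to estimate, and attaches a size and a duration to it. The two arms are not described in the same terms: one is credited with a gain on the primary outcomes, the other with knowledge.

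This matters because of how the outcomes are measured. The FACT-B and IES are questionnaires that the women answer themselves. The two apps have different names and visibly different content, and neither participants nor assessors are said to be blinded. If a woman learns that one app is expected to improve how she feels, her later answers can move with that expectation. A My Guide user may score herself better, and a control may be disappointed. Both shifts would appear in the analysis as a treatment effect.

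**Working it through.** **Claim against evidence in the documents**

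| Element of the Section 10.0 statement | What the documents offer in support |
|---|---|
| Benefit is likely | This is the hypothesis under test (Section 4.0). Section 2.0 reports earlier trials as underpowered or null, with one positive. Section 3.0 cites preliminary Aim 1c observations, but Aim 1c has no control arm. |
| Size is moderate to high | No effect estimate is given. The 0.63 SD in Section 13.0 is what the sample can detect, not an observed effect. |
| May last several years | The last Aim 2 assessment comes two weeks after the week-6 visit: 6 + 2 = 8 weeks. |

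**Route from wording to outcome**

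1. Consent comes first at the opening meeting, then the baseline questionnaires, then orientation to the assigned app (Section 4.0, Trial Design). Any benefit statement is therefore heard before baseline.
2. After orientation a woman knows which app she has. For bias in the comparison she must also expect more from one app than from the other.
3. ANCOVA adjusted for baseline (Section 13.0) does not remove a shift that differs between arms and arises after baseline.

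**The plan's own figure**

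Section 13.0 gives 40 per condition and 80% power for 0.63 SD. No significance level is stated, so two-sided 5% is assumed.

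- n per arm = 2 × (1.960 + 0.842)² / 0.63² = 15.70 / 0.397 = 39.6, rounded up to 40.
- Power at 40 per arm is 80.4% (normal) or 79.5% (t test). The figure reproduces.

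**Illustration of what a bias would do**

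The documents give no size for an expectancy shift. Let b be an assumed between-arm reporting bias in SD units, with no true effect. As a share of the design effect, 0.10 / 0.63 = 16% and 0.20 / 0.63 = 32%.

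The probability that the two-sided 5% t test rejects comes from the noncentral t distribution with 2n − 2 degrees of freedom and noncentrality b × √(n/2). For n = 40 and b = 0.2, the noncentrality is 0.2 × √20 = 0.894.

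| Assumed bias b (SD) | 40 per arm | 45 per arm |
|---|---|---|
| 0 | 5% | 5% |
| 0.1 | 7% | 8% |
| 0.2 | 14% | 16% |
| 0.3 | 26% | 29% |
| 0.5 | 60% | 65% |

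The 45 column is the planned allocation (90 randomised 1:1). These rates apply only to the part of the bias that differs between arms.

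**The case against.** The strongest reply is that Section 10.0 is protocol text and may never reach a participant. The consent form, brochure and scripts are not in the documents. A reader might infer that each woman is made to repeat a promise of sizeable, multi-year benefit. The documents do not show this: the benefits question is an example of a comprehension check, and the expected answer is not given. This part of the reply stands, so the bias argument has to be conditional.

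A reader might also infer that bias is built into the design. That does not follow either. The plan has an app control, the same procedures in both arms and the same stepped telecoaching rules, and no arm-specific consent is described. Knowing which app she has does not tell a woman that it is the favoured one. These features narrow any difference in expectation. They do not remove it if one arm's stated benefit is the primary outcome and the other's is knowledge.

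The wording is also partly hedged. Benefit and duration are both called potential, and the sentence names Aim 1c and Aim 2 participants rather than My Guide users alone. But the sentence concerns the intervention content, controls are treated separately, and the statement that benefit is most likely carries no such hedge.

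Finally, the reason given for the post-trial offer, that "even participants that were not assigned the intervention application (My Guide) have the opportunity to learn from it", might be read as telling women which app is favoured. It is the protocol's rationale and is not shown to be participant wording. The same section promises each arm access to the other app and says that My Health may be useful too. No change is needed there.

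**Conclusion.** The point holds in conditional form. Section 10.0 asserts a likely, moderate to high and potentially multi-year benefit that the documents do not establish, and an 8-week trial cannot support the duration. That much rests on the text alone.

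The risk of bias depends on the wording, or its substance, reaching women through consent, brochure or staff, and on the resulting expectation differing between arms. Neither can be confirmed from the documents. The size is unknown. The 0.1 to 0.2 SD range is an assumption, under which the false-positive rate would be about 7% to 14% at 40 per arm or 8% to 16% at 45. It would be too strong to conclude that a positive result could not be told apart from expectation. The change is worth making because it is cheap, removes an unsupported claim and lowers a real risk.

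**What to change.** - In Section 10.0, delete the statements that benefit is most likely, that it is moderate to high, and that it may last several years.
- Replace them, and the separate control paragraph, with one neutral statement for both Aim 2 arms: two health apps are being compared, either may or may not help, and it is not known which helps more.
- Use the same statement in the Section 7.0 discussion of benefits and as the accepted answer to the benefits question in the comprehension check.
- Check that the Aim 2 consent form, brochure and staff scripts match it in English and Spanish, and correct any that do not.

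The cost is a protocol amendment, re-translation of any participant text that changes, and a less attractive recruitment message. Sample size, procedures and analysis are unaffected.

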Planned Analyses Aim 2: Descriptive statistics will be used to characterize the overall sample and each condition. We will use Chi-square, Fisher’s exact tests, and Mann-Whitney U test for nonnormal data, as appropriate, to preliminarily examine differences in feasibility between the study conditions. While the sample sizes of 40 per condition will have 80% power to detect 0.63 standard deviations for our main outcomes. For all outcomes, change from baseline will be calculated and the mean changes within study condition will be converted to effect sizes. Effect sizes will be defined as the difference in means or proportions between the study conditions divided by the standard deviation of the outcome. Follow-up scores on the outcomes, HRQoL and cancer-specific distress, as well as all intervention targets, will be compared between study conditions, adjusted for baseline score, using analysis of covariance (ANCOVA). We will also reference established cutoffs for clinically meaningful differences for scores on the FACT, and FACT subscales, to identify ranges and patterns of change scores in HRQoL across the study conditions from study baseline to the follow-up assessments. Mixed effects models will be used to model the study outcome scores, and all intervention targets, over time for each group. Type of treatment, time since completion of active treatment, stage of diagnosis, education, marital status, language, comorbidities and age at diagnosis will be examined for their associations with study outcomes for potential entry as covariates in the statistical model.

14.0 Data Monitoring Plan to Ensure the Safety of Participants:

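### Do the two effect-size definitions for Aim 2 leave a standardised effect that can part company with the ANCOVA or mixed-model result?

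*Combined protocol and SAP*

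**What the plan says.** Section 4.0 (Procedures Involved, Specific Aim 2) names one model for FACT-B: "A longitudinal mixed effects linear model will be fit with the outcome". After a sentence on candidate covariates it adds: "Effect sizes will be calculated by dividing by the baseline standard deviation". It does not say what is divided.

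Section 13.0 (Planned Analyses Aim 2) makes four relevant statements:

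- For every outcome, "change from baseline will be calculated and the mean changes within study condition will be converted to effect sizes".
- The definition then follows: "Effect sizes will be defined as the difference in means or proportions between the study conditions divided by the standard deviation of the outcome".
- An ANCOVA with the baseline score as covariate compares the conditions at follow-up on HRQoL, cancer-specific distress and every intervention target.
- "Mixed effects models will be used to model the study outcome scores, and all intervention targets, over time for each group".

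For HRQoL, the plan will also refer to "established cutoffs for clinically meaningful differences for scores on the FACT, and FACT subscales".

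Section 4.0 (Trial Design) says that after the six weeks of application use "participants will complete two follow-up appointments", one at the end of week six and one two weeks later.

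**The concern.** Set side by side, the two sections leave three things open.

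1. **The SD.** Section 4.0 says baseline. Section 13.0 refers only to the outcome, which is measured at baseline and at two follow-ups.
2. **The numerator.** Section 13.0 could mean a difference in follow-up means or, because the preceding sentence concerns change from baseline, a difference in mean changes. When the baseline means differ by chance, neither equals the ANCOVA contrast.
3. **The model.** Section 4.0 mentions only the mixed model for FACT-B, while Section 13.0 plans both ANCOVA and mixed models. No sentence says which one supplies the effect size.

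Section 13.0 also moves from effect sizes built on within-condition changes to a between-condition definition in consecutive sentences.

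At stake is how the result is read. Effect sizes are planned for all outcomes. If numerator and SD were picked after the data were seen, the printed effect could look larger or smaller than the adjusted difference that was tested. Cancer-specific distress and the intervention targets are more exposed than HRQoL, because the plan names no clinical cutoff for them.

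**Working it through.** **Inputs from the documents.** 45 women per condition randomised 1:1 (Section 4.0); 80% power for 0.63 SD with 40 per condition (Section 13.0); assessments at baseline, week 6 and week 8 (Section 4.0).

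**Assumptions, because the documents give no values.** Two-sided 5% test; baseline-to-follow-up correlation ρ of 0.3, 0.5 or 0.8; follow-up SD equal to k times the baseline SD; equal variances in the two conditions.

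**Step 1: the plan's own figure.** Power = Φ(0.63 × √(40/2) − 1.96) = Φ(2.817 − 1.960) = Φ(0.857) = 0.804. With the noncentral t distribution it is 0.795. The stated 80% is reproduced. It does not depend on how the observed effect is later standardised for reporting.

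**Step 2: size of a chance baseline imbalance.** The standard error of the difference in baseline means is √(2/45) = 0.211 SD. An imbalance at least this large arises in about one trial in three (P(|Z| > 1) = 0.317).

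**Step 3: departure from ANCOVA, taking k = 1 and an imbalance b = 0.211.**

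- Raw follow-up difference minus ANCOVA estimate = ρb
- Difference in mean changes minus ANCOVA estimate = −(1 − ρ)b
- 95% half-width of the ANCOVA estimate ≈ 1.96 × 0.211 × √(1 − ρ²)

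| ρ | Raw minus ANCOVA | Change minus ANCOVA | 95% half-width |
|---|---|---|---|
| 0.3 | 0.063 | −0.148 | 0.39 |
| 0.5 | 0.105 | −0.105 | 0.36 |
| 0.8 | 0.169 | −0.042 | 0.25 |

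The two unadjusted readings differ from each other by ρb + (1 − ρ)b = b = 0.211 SD at any correlation, and by nothing when the baseline means are equal. A simulation of 20,000 trials at each correlation, with the ANCOVA slope estimated, gave SDs for these departures of 0.066, 0.107 and 0.169 (raw) and 0.149, 0.107 and 0.044 (change), in line with the formulas. With 40 per condition the standard error is √(2/40) = 0.224, so the departures grow by a factor of 0.224/0.211 = 1.06.

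**Step 4: choice of SD.** Dividing by the follow-up SD instead of the baseline SD multiplies the effect by 1/k: 1.11 at k = 0.9, 1.00 at k = 1 and 0.91 at k = 1.1. Over a wider assumed range, an effect of 0.63 becomes 0.63/0.8 = 0.79 or 0.63/1.2 = 0.53.

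**Step 5: do the sentences conflict?** Section 13.0 supplies a numerator (a between-condition difference) and an SD of the outcome. Section 4.0 says which SD. The SD of the outcome score at baseline meets both. Section 4.0 also rules out the SDs that would inflate the figure most. At ρ = 0.8 and k = 1, the SD of change is √(2 − 1.6) = 0.632 and would turn 0.63 into 1.00. The ANCOVA residual SD is √(1 − 0.64) = 0.6 and would give 1.05. Neither is a baseline SD.

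**The case for a change.** The best case for a change is that fixing the denominator settles only half of the definition. The numerator is still unstated in Section 4.0 and open in Section 13.0, and the two unadjusted readings can differ by 0.21 SD, a third of the 0.63 SD used for power (0.211/0.63 = 0.33). One aligned sentence would cost almost nothing.

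Part of this stands. The definition is incomplete, and the step from within-condition to between-condition effect sizes in Section 13.0 is loosely written. The departures can also exceed those tabulated. At an imbalance of two standard errors (P(|Z| > 2) = 0.046) they double, and at ρ = 0.8 the raw follow-up difference would be 2 × 0.169 = 0.34 SD from the ANCOVA estimate, outside its 0.25 SD half-width.

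The objection does not carry further, for three reasons.

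- The 0.21 SD gap lies between the two unadjusted readings. Measured against the ANCOVA estimate, which is the test in question, each is nearer.
- Under randomisation, and without differential loss to follow-up, the raw, change-score and ANCOVA differences at a given visit have the same expectation. The divergence is chance variation and does not push the result towards either condition.
- A substitute sentence that took the difference from whichever model is reported would leave the choice between ANCOVA and mixed model open. It would also assume that the mixed-model contrast is baseline-adjusted, which the documents state only for ANCOVA. If confined to continuous scores with one between-condition definition, it would leave proportions undefined and drop the within-condition standardised change that Section 13.0 provides for.

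**Conclusion.** The concern describes the text accurately but does not call for a change. The two sections are incomplete and do not contradict each other. The baseline SD of the outcome fits both, and the sentence order in Section 4.0 points naturally to the model estimate as the quantity divided by it. The hypothesis tests, their p-values and the stated power are untouched. The baseline-adjusted comparison is prespecified for HRQoL, cancer-specific distress and every intervention target, so a reader will have the adjusted difference alongside any standardised figure. For HRQoL the FACT cutoffs give a second yardstick.

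What remains is a possible gap between a descriptive effect size and the ANCOVA estimate of about 0.04 to 0.17 SD, plus about 10% from the choice of SD. These figures assume 45 women analysed per condition, equal variances, a one-standard-error baseline imbalance, correlations of 0.3 to 0.8 and SD ratios of 0.9 to 1.1. The gap disappears when the baseline means and the SDs are equal. An analyst can fill this when writing up, by stating which difference and which SD were used at each visit and by labelling any within-condition standardised change as such.
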